The level-2 models are used to test whether time-invariant predictors are related to the initial status and the change of the outcome over time. The treatment effect in this study will be coded as a dummy variable, a time-invariant predictor of change to be evaluated in the level-2 models. Other examples of time-invariant predictors include socioeconomic status, parent marital status, and gender that are thought to be stable over time, and will be tested as the moderators of the treatment effect. Specifically, the level-2 models are

$$\begin{aligned}\pi_{0i} &= \beta_{00} + \beta_{01} * X_i + \mu_{0i} \\ \pi_{1i} &= \beta_{10} + \beta_{11} * X_i + \mu_{1i}\end{aligned}$$

where β_{00} and β_{10} are the grand means for the intercepts and the slopes estimated in the level-1 model, respectively. β_{01} and β_{11} are regression coefficients for X_i which is a time-invariant variable for subject i , with μ_{0i} and μ_{1i} the random errors in the models. When X_i is the treatment effect coded as a dummy variable, a significant β_{01} indicates that the outcome variable is different for the treatment groups at the baseline. Our major research interest is to evaluate coefficient β_{11} ----- a significant β_{11} shows that the change in the outcome variable is different for treatment groups due to the intervention program.

Both the basic level-1 and level-2 models in IGM can be extended by including more variables in the models. In general, variables measured repeatedly over time, also referred to as time-varying or within-subject variables, are included in level-1 models. The between-subject variables, also referred to as time-invariant variables and usually only measured at baseline, are included in level-2 models. The shape of the curves for the outcome variables will be determined first. Time-invariant and time-varying predictors will then be examined for their relationship with the outcome using the estimated growth factors of the trajectories. The 3 primary hypotheses proposed in this study will be evaluated within the IGM framework. SAS Proc Mixed and Proc Glimmix will be used for the IGM analysis for the 3 primary hypotheses.

Hypothesis 1: Adolescents in CGS+BT will show more improvement in glycemic control (HbA_{1c}; Kovatchev's measures of glycemic variability derived from SMBG and CGS data; Proportion of CGS values in the normal range) compared with those in SC and CGS over the 9-month Randomized Phase.

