The IGM approach allows for comparison and selection of the appropriate covariance structure of the outcome measured over time. Candidate structures include compound symmetry (CS), autoregressive order-1 AR(1), unstructured, and AR(1) with random effect which will be specified in SAS Proc Mixed. The AIC and BIC indices will be used for model selection, with smaller AIC or BIC values indicating relatively better models fitting the data. The selection of an appropriate covariance structure may further reduce the bias of model estimation.

Hypothesis 2: Youths in CGS+BT will realize more improvement in diabetes-related behavioral outcomes (Diabetes Self-Management Profile; PedsQL Diabetes Module; Diabetes Responsibility and Conflict Scale; Hypoglycemia Fear Survey; Blood Glucose Monitoring Communication Questionnaire; Blood Glucose Monitoring System Rating Questionnaire) compared with those in SC and CGS over the 9-month randomization phase of the study.

The data analysis strategy to evaluate Hypothesis 2 will be similar to that applied to Hypothesis 1 within the IGM framework. Specifically, in the level-1 model the outcome variables will be the Diabetes Self-Management Profile, the PedsQL Diabetes Module, the Diabetes Responsibility and Conflict Scale, the Hypoglycemia Fear Survey, the Blood Glucose Monitoring Communication Questionnaire, and the Blood Glucose Monitoring System Rating Questionnaire. The Time variable in the level-1 model will be the time interval from baseline to the time of measurement in month. In level-2 models, a dummy variable indicating treatment groups will indicate the treatment effect. A significant coefficient of the dummy variable will show that the change rate of the outcome is different for the treatment groups due to the treatment program.

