To adjust for the effects of important covariates in examining the treatment effect, the covariates will be included in level-1 and level-2 models. The time-varying covariates will be included in the level-1 model and the time-invariant covariates will be in level-2 models. There are two advantages of adjusting the covariates when evaluating the treatment effect. First, the adjusted analysis will improve the power of evaluating the treatment effect because of increased precision of estimation.¹⁶³⁻¹⁶⁵ By adjusting a covariate in a linear model, the precision gained is proportional to the correlation between the covariate and the outcome variable. Second, omitting important covariates in the model may lead to bias of the results. Therefore, important covariates will be included in the models to evaluate the group difference in all the outcomes. Similar to the strategies in Primary Hypotheses 1, the effect of site difference will be treated as an additional between-subject variable as a random effect in the models.

Hypothesis 3a: Improvements in HbA_{1c} during the 9-month Randomized Phase will be moderated by adolescents' baseline status on the following measures: Socioeconomic status; Family composition; Adolescent age; Parent-Adolescent Relationship Questionnaire; Diabetes Family Responsibility Questionnaire; Wiebe Parental Supportive Involvement Interview; and Diabetes Responsibility and Conflict Scale).

Analysis of moderator effects can identify variables that are predictive of intervention outcomes. . For example, in Hypothesis 3a, if the treatment effect on HbA_{1c} differs as a function of the family's socioeconomic status, then socioeconomic status is a moderator variable. It is important to evaluate the heterogeneity of the treatment effect to identify the subgroups that derive lesser or greater benefit from the intervention.

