Mediators are process variables that are affected by the treatment effect and are believed to have effects on the outcome. Mediator analysis will help us to understand the mechanisms why the treatment is effective. In mediator analysis we will determine whether the treatment effect is wholly or partial due to the mediators. Following Baron and Kenny,¹⁶⁶ traditional mediator analysis using cross-sectional data involves three regression equations, the outcome regressed on the treatment effect, the outcome regressed on both the treatment and the mediator, and the mediator regressed on the treatment. In the multi-level modeling framework, Krull & MacKinnon¹⁶³ introduced a detailed process of mediator analysis that has advantages over the methods used in the context of cross-sectional data. We will closely follow the approach recommended by Krull & MacKinnon¹⁶³ to examine the possible mediators proposed in Hypothesis 3b.

Specifically, in the IGM framework described above, HbA_{1c} will be the outcome in level-1 models and the treatment effect will be a dummy variable indicating treatment groups in level-2 models. Since all mediating variables in this study (the Diabetes Self-Management Profile, Diabetes Responsibility and Conflict Scale, Wiebe Parental Supportive Involvement Interview, and Blood Glucose Monitoring Communication Questionnaire) are within-subject variables measured repeatedly during the study, these mediators will be included in the level-1 model. Following Krull & MacKinnon,¹⁶³ the mediator analysis involves three stages of IGM: HbA_{1c} predicted by treatment alone, HbA_{1c} predicted by both treatment and the mediator, and the mediator predicted by the treatment alone. Combining the results from the three stages of IGM, we can determine if a candidate is a whole, partial, or non-mediator of the treatment effect in improving HbA_{1c}.

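### Section 5.12 sends time-varying covariates into the Hypothesis 2 treatment-effect models without excluding those that treatment can change, and names no primary model

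*Combined protocol and SAP*

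**What the plan says.** All references are to the combined protocol and SAP.

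- **Section 5.12, general model.** The plan states that "variables measured repeatedly over time, also referred to as time-varying or within-subject variables, are included in level-1 models".
- **Section 5.12, Hypothesis 1.** The treatment dummy is tested first. If the groups differ significantly, a covariate-adjusted model asks whether the difference survives. The examples are demographic and disease-history variables, in an open list. Site is a random effect.
- **Section 5.12, Hypothesis 2.** The strategy is described as similar to that for Hypothesis 1, and "a dummy variable indicating treatment groups will indicate the treatment effect". The plan then adds: "To adjust for the effects of important covariates in examining the treatment effect, the covariates will be included in level-1 and level-2 models". It continues: "The time-varying covariates will be included in the level-1 model and the time-invariant covariates will be in level-2 models". One reason given is that "omitting important covariates in the model may lead to bias of the results", and the conclusion is that "important covariates will be included in the models to evaluate the group difference in all the outcomes".
- **Section 5.12, Hypothesis 3b.** Mediators are defined as variables that treatment affects. They are measured repeatedly, and "these mediators will be included in the level-1 model". One stage of that analysis is "the mediator predicted by the treatment alone".
- **Section 5.9.** Baseline values are compared for significant group differences, to decide whether adjustment is needed.
- **Sections 5.3 and 5.8.** Randomization is stratified by center and by HbA1c at 8.8%. The HbA1c stratum appears in no model in section 5.12.

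**The concern.** Specific Aim 2 asks whether adding the behavioral intervention changes behavioral outcomes. That is a question about the effect of assignment. A covariate measured after randomization can carry part of that effect, and adjusting for it removes that part. The Hypothesis 3b analysis enters variables at level 1 for exactly this purpose. The Hypothesis 2 text uses the same position in the model while claiming to estimate the treatment effect itself, and has no rule to keep the two uses apart.

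Two further gaps make this matter more. The bias argument encourages wide adjustment where randomization already removes the need for it. And because no Hypothesis 2 model is named as primary, the choice between an unadjusted and an adjusted result stays open until the data are seen.

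**Working it through.** **1. Which repeated variables could enter level 1?** The section 5.7 schedule has 17 rows, of which two are baseline only (General Information Form, Diabetes Problem Solving Interview). The other 15 are:

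- 5 glycemic outcomes or their source data: meter downloads, CGS downloads, variability measures, HbA1c, blinded CGS;
- 6 Hypothesis 2 outcomes: self-management profile, monitoring-system rating (taken to be the Hypothesis 2 rating questionnaire), monitoring communication, hypoglycemia fear, responsibility and conflict, PedsQL;
- 1 secondary outcome under Specific Aim 1: hypoglycemia diary;
- 1 Hypothesis 3b mediator that is not also an outcome: parental involvement interview;
- 1 scale that section 5.5 says will be used to see whether CGS changes it: family responsibility;
- 1 collected in CGS+BT only: readiness to change.

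5 + 6 + 1 + 1 + 1 + 1 = 15. Three of the six Hypothesis 2 outcomes are also Hypothesis 3b mediators. Section 5.5 adds other quarterly variables: Tanner stage, height, weight, BMI, growth velocity and regimen details. Some, such as Tanner stage, are much less open to change by treatment.

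**2. Does omitting a covariate bias the comparison?** Let Y = a + τA + γC + e, with A randomized.

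- If C is fixed before randomization, it is independent of A. Omitting it leaves the expected coefficient of A at τ, and the cost is precision.
- If treatment shifts C by δ, the effect of assignment is τ + γδ. Adjusting for C returns τ only.

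So, missing data aside, the bias argument does not support adjustment for post-randomization variables.

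**3. How large could the distortion be?** The plan gives no effect size or covariate for Hypothesis 2, so this is an HbA1c illustration only.

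Inputs from section 5.13: SD 1.2 at baseline and 1.5 at month 12; a 0.8-point difference between CGS and CGS+BT at month 12; 50 per arm. Assumed: linear effect, zero intercept-slope covariance, residual variance 0.3 (range 0.2 to 0.4), no dropout, and a covariate with within-person variance 0.3 and between-person variance 0.7 that treatment shifts by 0.6 at month 9.

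- Slope variance: (2.25 − 1.44)/144 = 0.005625.
- Check against the plan: 0.8/1.5 = 0.533, as stated. Over five visits (Sxx = 90), SE = √[(2/50) × 144 × (0.005625 + 0.3/90)] = 0.227. Power for 0.8 is 94.1% (stated 94.5%). Power for the 0.6-point SC versus CGS contrast is 75.2% (70.2 to 80.6% over the range; stated above 80%). The inputs match the plan only roughly.
- Month-9 effect: 0.8 × 9/12 = 0.6. Month-9 SD: √(1.44 + 81 × 0.005625) = 1.377, so 0.6 is 0.44 SD.
- Unadjusted SE, visits 0 to 9 (Sxx = 45): √[(2/50) × 81 × (0.005625 + 0.3/45)] = 0.200. Power: Φ(0.6/0.200 − 1.96) ≈ 85%.
- Adjusted, with the outcome's total variance held at these values and the covariate carrying a share s: effect 0.6(1 − s), remaining residual variance 0.3 − 0.3s².

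| Share s | Adjusted effect | Residual variance | SE | Power, closed form | Power, simulated |
|---|---|---|---|---|---|
| 25% | 0.45 | 0.281 | 0.196 | 63% | 62% |
| 50% | 0.30 | 0.225 | 0.186 | 37% | 37% |
| 75% | 0.15 | 0.131 | 0.166 | 15% | 16% |

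The closed form ignores error in the covariate's coefficient. Simulation runs differ by a point or two. With residual variance 0.2 (remaining 0.2 − 0.3s²), the closed form gives 91% unadjusted and 72/44/18% adjusted; with 0.4 (remaining 0.4 − 0.3s²), 79% and 56/31/13%.

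The distortion need not be toward zero. A covariate acting against the effect (s = −25%) gives 0.6 × 1.25 = 0.75. In simulation, a covariate that treatment shifts, with no causal effect but a within-person residual correlation of +0.3 or −0.3 with the outcome, gives about 0.44 or 0.75. One that treatment shifts but that is unrelated to the outcome leaves 0.60.

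**4. What would the stratum add?** For HbA1c, simulated REML fits give no reduction in SE with the stratum on the intercept only, and 0.9 to 1.9% with it on intercept and slope.

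**The case against.** The level-1 sentence can be read as bookkeeping: it says where each type of covariate sits in a two-level model. The only adjustment covariates named as examples are demographic or disease history, and Hypothesis 2 is said to follow a similar strategy. Mediators have their own analysis under Hypothesis 3b, so the authors know that treatment changes some variables. A reader might infer from the text that a mediator will be adjusted for. The documents do not support that: no time-varying covariate is named.

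A reader might also infer that no unadjusted Hypothesis 2 result is planned. That too goes too far. The Hypothesis 1 order (test first, adjust afterwards) and the plain dummy-variable test under Hypothesis 2 suggest an unadjusted test first. Hypothesis 3b also models three of the Hypothesis 2 outcomes on treatment alone.

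What stands after this: the Hypothesis 2 text says covariates will be included, says time-varying ones go in at level 1, and extends adjustment to all outcomes. The named examples belong to Hypothesis 1, form an open list, and mostly belong at level 2, so they do not show what would enter at level 1. The implied order of tests conflicts with the later statement, and neither result is called primary.

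It is also fair that a remedy should not discard useful baseline covariates. Variables such as SES or diabetes duration, fixed before randomization, can stay for precision.

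**Conclusion.** The point holds as a missing restriction together with a missing designation of the primary model. It is not a demonstrated error in a planned analysis. If a covariate that treatment changes, and that is related to the outcome, enters the model, the coefficient is not the effect of assignment; it usually moves toward zero but can move away from it.

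The size for Hypothesis 2 cannot be given. The illustration shows that loss of effect and power could be large, but it uses HbA1c inputs, an assumed covariance structure and an assumed covariate. It does not show that the plan's power figures are wrong.

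Two smaller points stand separately and do not drive the severity: baseline adjustment depends on significance tests, and the HbA1c stratum used in randomization is in no model. The gain from adding the stratum is small, about 0 to 2% off the SE for HbA1c. The change is worth making because it is cheap and settles the Hypothesis 2 analysis before data are seen.

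**What to change.** - **Section 5.12, Hypotheses 1 and 2.** State that the primary treatment-effect models adjust only for pre-specified variables fixed at or before randomization. Always include center (as the random effect already planned) and the HbA1c randomization stratum, whatever any test shows. Other named pre-randomization covariates, such as SES or diabetes duration, may be kept for precision.
- **Section 5.12, Hypothesis 2.** Name this model as the primary Hypothesis 2 analysis. Remove the sentence placing time-varying covariates in level 1 of the treatment-effect models, and the bias argument with it.
- **Post-randomization variables.** Keep them for Hypothesis 3b and the analyses in section 5.11.
- **Section 5.9.** Delete the significance-test trigger for baseline adjustment.
- **Stratum definition.** Use the stratum as randomized. The introduction to the resubmission puts a value of exactly 8.8% in the high stratum, and sections 5.3 and 5.8 put it in the low one; reconcile these.

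Cost: wording only. No change to data collection, visits or sample size, and no planned mediation analysis is lost.

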To evaluate the treatment effects on the change of glycemic control over time, HbA_{1c} measured from baseline to end of study will be the outcome variable in the level-1 model. A participant without missing values will have a total of 5 measures of HbA_{1c}. The time interval between baseline and the measure of each HbA_{1c} in the unit of months will be the Time variable in the level-1 model. The shape of the HbA_{1c} trajectory will be determined statistically by comparing a linear model and a quadratic model using the AIC and BIC indices produced by SAS Proc Mixed. In level-2 models, X_i will be a dummy variable indicating treatment groups. For example, to evaluate the treatment effects between CGS+BT and CGS groups, the dummy variable will be coded 1 for CGS+BT and 0 for CGS. A significant coefficient of the dummy variable will indicate that the change rate of HbA_{1c} over time is different for the two groups due to the treatment effect. A similar strategy will be applied to evaluate the difference in the change of HbA_{1c} between CGS+BT and SC, and CGS and SC groups. Since Kovatchev's measures of glycemic variability and the proportion of CGS values in the normal range are on continuous scales that are comparable across repeated measures, these variables are also appropriate to use as outcome variables with IGM estimated using SAS Proc Mixed.

If the treatment groups are significantly different in the outcome measures, it is of interest to examine whether the difference in treatment groups persists after adjusting the covariates that are known to be associated with the outcome. This process will be conducted by including covariates in the IGM framework. For example, demographic variables (SES, parent marital status, etc.) and disease variables (diabetes onset age, duration, etc.) can be included in the models as covariates to improve the precision of estimation when evaluating the treatment effect. If the dummy variable is still significant with the covariates in the model, the interpretation is that the treatment accounts for some unique variance in the change of the outcome over time above and beyond the effects of the covariates. The effect of site difference will be included as a between-subject covariate with a random effect. Specific programming to include the site difference as a random effect using SAS Proc Mixed will follow Dmitrienko et al for clinical trial data collected from multiple sites.¹⁶²

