The testing of moderators will be conducted within the IGM framework outlined above. Specifically, HbA_{1c} will be the outcome and Time will be measured in months in the level-1 model. A dummy variable indicating treatment groups will be the predictor in level-2 models. A product term of the proposed moderator and the dummy variable, together with the main effect of the moderator candidate, will be entered into the level-2 models. A significant coefficient of the product term indicates that the candidate is a significant moderator. The analysis process will be carried out using Socioeconomic Status, Family composition, adolescent age at baseline, and scores on the Diabetes Problem Solving Interview, Parent-Adolescent Relationship Questionnaire, Diabetes Family Responsibility Questionnaire, Wiebe Parental Supportive Involvement Interview, and Diabetes Responsibility and Conflict Scale separately to determine significant moderators.

To interpret the effects of any significant moderators, estimated individual growth factors (e.g., the slope in linear trajectory) will be compared among subgroups of the moderator. The analysis will reveal subgroup differences in the change of outcome due to the treatment effects. For moderators measured on continuous scales, such as adolescent age at baseline, appropriate categorization will be applied for meaningful interpretation of the findings. Important covariates will be included in the models to adjust the possible effects

[figure not shown]
of the covariates. Within this model, site differences will be treated as a between-subject covariate to adjust for its possible effects on the outcome.

Hypothesis 3b: Improvements in HbA_{1c} during the 9-month Randomized Phase will be mediated by improved scores on the Diabetes Self-Management Profile, Diabetes Responsibility and Conflict Scale, Wiebe Parental Supportive Involvement Interview, Diabetes Problem Solving Interview, and Blood Glucose Monitoring Communication Questionnaire.

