5.13. Sample size and statistical power. Power analysis and sample size estimation were based on projected treatment effects on HbA_{1c}, the primary outcome measure, as shown in the figure below. To estimate sample sizes needed in the three groups for sufficient statistical power, a Monte Carlo simulation study was conducted using MPlus (Version 5).¹⁶⁴ The Monte Carlo procedure is the most common and the preferred methodology to estimate sample size in Individual Growth Modeling.¹⁶⁷⁻¹⁶⁸ In a Monte Carlo study, random samples are generated repeatedly using the known population parameters with a specified sample size. The percentage of simulated samples that have reached significance on the parameters is the estimated power of the study. Thus, the required sample size can be determined accurately by varying sample sizes in a series of simulations. MPlus provides extensive facilities for conducting Monte Carlo studies on IGM. Our simulation study followed the procedures recommended by Muthen & Muthen,^{164, 168} including generating missing values to reflect expected attrition and the pattern of missing data in the proposed study. The primary contrast of interest in this study is change in HbA_{1c} relative to baseline values among adolescents in the SC,

CGS, and CGS+BT groups. Based on the mean HbA_{1c} obtained in several prior trials at Nemours Children's Clinic in Jacksonville and the stated enrollment criteria, we expect that the baseline mean and standard

deviation values will be approximately $8.8\% \pm 1.2\%$. The standard deviation of HbA_{1c} will increase gradually with each measure spaced about 3 months. At the end of 12 months, we expect a 0.8% difference in HbA_{1c} between the CGS and CGS+BT groups. Assuming a standard deviation of approximately 1.5% at the end of the study, the effect size will be 0.533, a moderate effect size as defined by Cohen¹⁶⁹ that is clearly clinically significant. Based on the retention rates in our NIH-funded randomized trials, we anticipate an attrition rate <10% during the 1-year study. Therefore, enrollment of 150 patients (50 per group) should result in at least 135 (45 per group) at the end of the 9-month randomization phase of the study. We anticipate that about 120 participants (40 per group) will complete the 3-month Continuation Phase of the study.

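### Significant moderators are to be interpreted by comparing estimated individual slopes between subgroups; if these are empirical-Bayes slopes, the reported subgroup effects will look too precise or too small

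*Combined protocol and SAP*

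**What the plan says.** Section 5.12, under Hypothesis 3a, has two steps. The first is the test: "The testing of moderators will be conducted within the IGM framework outlined above". The moderator and its product with the treatment dummy enter the level-2 equations, and "A significant coefficient of the product term indicates that the candidate is a significant moderator".

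The second is interpretation, and applies only to moderators already found significant: "estimated individual growth factors (e.g., the slope in linear trajectory) will be compared among subgroups of the moderator". The next sentence presents this as the step that shows how the treatment effect on change differs between subgroups. For continuous variables, "For moderators measured on continuous scales, such as adolescent age at baseline, appropriate categorization will be applied for meaningful interpretation of the findings"; no cut-points are given.

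The same section defines the level-1 slope separately for each subject and names SAS Proc Mixed as the software. It does not say whether the slopes to be compared are empirical-Bayes predictions, per-subject least-squares fits or model-estimated subgroup slopes. Nor does it say which fitted model supplies them, or whether a standard error, interval or test will accompany the comparison.

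**The concern.** An empirical-Bayes slope is a weighted average of the youth's own data and the model's expectation for that youth. Comparing such slopes between subgroups as if they were observations goes wrong in one of two ways.

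- If the supplying model contains the moderator and the product term, each slope is pulled toward its own subgroup mean. The subgroup means are right, but the spread around them is too small, and so is any standard error computed from that spread.
- If the supplying model omits the moderator, slopes are pulled toward a mean shared by the subgroups. The difference between subgroups is then itself shrunk.

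At stake is the message to readers about which adolescents gain more or less from CGS or CGS+BT, and how firmly that is known.

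**Working it through.** **Inputs from the documents (Section 5.13).** 50 per group; HbA1c SD 1.2% at baseline and about 1.5% at the end; a 0.8% CGS versus CGS+BT difference at 12 months; visits at 0, 3, 6, 9 and 12 months; stated power 94.5%.

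**The plan's own figures.** 0.8/1.5 = 0.533, as stated: "Assuming a standard deviation of approximately 1.5% at the end of the study, the effect size will be 0.533". The 94.5% does not follow from a two-mean comparison at the end point, which gives 66%, 72% and 76% two-sided for 40, 45 and 50 per group. A growth model can reach it, but the variance components are not stated, so it can be neither confirmed nor refuted. It is used here only to choose plausible variance components.

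**Assumptions.** Two-sided 5% level, an evenly split binary moderator (25 per cell), complete data, linear change. Residual variance s² is not given and is varied from 0.1 to 0.5.

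**Variance of a subject's slope, per 12 months.** With time in years, the five visits have a sum of squared deviations of 0.625. So V = τ² + s²/0.625, where τ² is the true slope variance.

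- Power of 94.5% at 50 per group needs V ≈ 1.264: SE = √(2 × 1.264/50) = 0.225; 0.8/0.225 = 3.56; 3.56 − 1.96 = 1.60; Φ(1.60) ≈ 0.945.
- The rise in variance from 1.44 to 2.25 requires τ² + 2c = 2.25 − 1.44 = 0.81, where c is the intercept-slope covariance. This fixes c for each τ².
- Slope reliability = τ²/V. For s² = 0.3: τ² = 1.264 − 0.48 = 0.784, and 0.784/1.264 = 0.62.

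**Correct standard error of the subgroup difference in treatment effect.** Four cells of 25: √(4 × 1.264/25) = 0.45.

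**Simulation, 3,000 trials per setting, true subgroup difference 0.80% per 12 months or zero.**

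| s² | τ² | Reliability | Correct SE | SE from EB slopes, moderator in model | Shortfall | Coverage of 95% CI | Estimate of 0.80, moderator omitted |
|---|---|---|---|---|---|---|---|
| 0.1 | 1.10 | 0.87 | 0.45 | 0.39 | 13% | 91% | 0.71 |
| 0.3 | 0.784 | 0.62 | 0.45 | 0.28 | 37% | 78% | 0.53 |
| 0.5 | 0.464 | 0.37 | 0.45 | 0.19 | 57% | 60% | 0.36 |

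With the moderator in the supplying model, the estimate itself is unbiased (0.80). With it omitted (arm retained), type I error stays near 5%, but the effect is attenuated. Per-subject least-squares slopes and the growth model's own contrasts were both unbiased, with about 95% coverage throughout.

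**Four visits.** Hypothesis 3a is worded for the 9-month Randomized Phase. Visits at 0, 3, 6 and 9 months have a sum of squares of 0.3125, so at s² = 0.3 reliability falls to 0.784/(0.784 + 0.3/0.3125) = 0.784/1.744 = 0.45. The shortfall is close to one minus reliability, so it grows.

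**How plausible is the mild end?** Section 5.5 gives an assay coefficient of variation of 2-3%. At a mean of 8.8%, that is an SD of 0.18-0.26, or a variance of 0.03-0.07. With s² = 0.1, only 0.03-0.07 is left for all other departure from a straight line, so the 13% case looks optimistic.

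**The case against.** The strongest reply is that shrinkage is inferred. The method is called Individual Growth Modeling, so the word individual may be loose, and the phrase could mean least-squares slopes or model-estimated subgroup slopes. The first shows no fault with balanced data; the second is essentially the remedy. This stands as a limit on certainty. Still, with a slope defined for each subject and Proc Mixed as the software, empirical-Bayes slopes are the natural reading, and nothing in the text excludes them.

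Second, no error bars are mentioned. A purely descriptive comparison of means from the model containing the moderator would be correct. That also stands, but subgroup effects would then be reported with no measure of uncertainty.

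Third, the moderator is already in the level-2 model when interpretation begins, so the attenuated branch is the less natural one. Agreed; the text leaves the supplying model open.

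Fourth, some candidate covariance structures in Section 5.12 (compound symmetry, AR(1), unstructured), if fitted without random effects, yield no individual slopes. True, but the step would then be undefined.

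Two stronger readings are tempting. A reader might infer that false moderators will be declared, since a 5% test on empirical-Bayes slopes from the moderator model rejects in 9%, 22% or 40% of null trials in the three settings. The documents do not support this: they specify no such test, moderation is declared from the product term, and the step follows only a significant one. A reader might also take the general sentence in Section 5.12, "Time-invariant and time-varying predictors will then be examined for their relationship with the outcome using the estimated growth factors of the trajectories", as proof that the whole plan runs in two steps. It can equally describe ordinary conditional growth modelling, in which predictors of intercept and slope are estimated jointly, so it is not relied on here.

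**Conclusion.** The point holds conditionally and concerns interpretation only. If the compared slopes are empirical-Bayes predictions, the step understates standard errors by about 13% to 57% with five visits, and by more with four, when the moderator is in the supplying model. It shrinks a true 0.80% difference to about 0.36-0.71% when the moderator is left out. Where in those ranges the trial would fall depends on a residual variance the documents do not give; the other assumptions are 50 per arm, an even binary moderator and complete data. It would go too far to say that the error bars will certainly be far too narrow. The product-term test of Hypothesis 3a and the primary analysis stand as they are. The change is worth making because the model already to be fitted supplies a better answer under every setting tried.

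**What to change.** In Section 5.12, Hypothesis 3a, replace the comparison of individual growth factors with this: for each significant moderator, report the treatment effect on slope within each subgroup, and the difference between subgroups, with 95% confidence intervals, as contrasts (ESTIMATE statements) from the same fitted model that contains the product term. For continuous moderators, evaluate the contrasts at values stated in advance rather than in categories chosen later. Keep individual predicted slopes for display only.

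The cost is a sentence or two of SAP wording and a few lines of SAS. No extra data are needed, and it is less work than a second-step comparison.
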